6.2.2. Platelet Component Preparation for Block Administration

- This study will only utilize platelet components collected in the NIH Clinical Center, Department of Transfusion Medicine
- Only IBS platelet components that are >4.4×10¹¹ platelets, as measured from a sample obtained from the storage container post-transfer from the compound adsorption device (CAD) container, will be used; this number was selected in order to closely approximate the number of platelets transfused during routine issue of a single dose of platelets
- 2 ml will be withdrawn into a sample pouch or tubing segment, heat sealed, detached, and then emptied into a labeled EDTA tube to be submitted to CPS for platelet count determination
- Each component will be split by dividing the tubing at the point of union, into two, roughly equal, "doses", following established TSL procedures (TSL-SOP-3941)
- Each dose will have its weight documented in order to calculate the number of platelets in each dose
- Each block consists of two doses from one platelet product, one for a Long Transfusion duration and one for a Short Transfusion duration:
- Both doses will be gently swirled for ~20 revolutions, every 30-minutes, to thoroughly mix the product; this will done by the nursing staff
- Both doses will be weighed to ascertain volume
- One dose within each block will be transfused over a LONG duration, over 4-HOURS from the time the back is spiked and one dose within each block will be transfused over a SHORT duration, within 60-minutes from the time the bag is spiked; both transfusions may occur via an infusion pump or by gravity.

6.3. Treatment Monitoring

6.3.1. CBC Collection

All CBC blood draws will be collected in a 2 ml EDTA tube, after wasting the first 1ml of blood drawn. The sample should be obtained via the patient's peripheral access device, but a peripheral venipuncture or draw from the patient's central access device may be done if access the patient's peripheral line is not feasible. The initial 1 ml sample discard, prior to filling the 2ml EDTA tube, is to prevent a false reading by drawing the sample from the same line through which the patient is receiving the transfusion.

Patients will have platelet counts obtained by CBCs collected at the following scheduled intervals:

- 1) Pre-transfusion (0-HOUR) CBC: obtained 15-minutes prior to transfusion start time
- 2) 2-HOUR CBC: Obtained +/- 15-minutes of the 2-HOUR mark after the infusion start time

- 3) 4-HOUR CBC: Obtained +/- 15-minutes of the 4-HOUR mark after the infusion start time
- 4) 6-HOUR CBC: Obtained +/- 15-minutes of the 6-HOUR mark after the infusion start time. Also serves as the PRE (0-HOUR) CBC for the subsequent, transfusion; the subsequent transfusion will also have scheduled CBCs drawn at q2hr intervals (i.e. CBC at 8-HOUR, 10-HOUR, 12-HOUR), collected +/- 15-minutes of each time mark)

CBCs unable to be obtained as indicated will result in an unsuccessful, or "failed," block. Failed blocks will be precluded from further analysis. All attempts will be made to repeat the block as soon as clinically possible. Blood draws for other clinical purposes should be avoided, but will not result in a failed block unless it/they preclude the aforementioned scheduled CBCs needed for this protocol's treatment monitoring.

From the CBC, platelet value will be used to calculate the platelet AUC using the trapezoid rule and adjusted for the absolute number of platelets transfused, on a rolling basis for each transfusion.

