Taken altogether, these data support slow, continuous transfusion as a potential transfusion approach that may minimize the number and/or duration of adverse hemorrhagic events and that may result in greater platelet increments per unit time than the conventional infusion approach. Furthermore, there is no evidence in the published literature or any reported relevant experience of physicians who treat thrombocytopenic patients to suggest that CPT would be deleterious. Therefore there is equipoise in this trial design.

This study only utilizes Cerus Intercept Blood System (IBS) single, apheresis donor platelets (SDP) to compare two treatment approaches: 4-HOUR continuous infusion ("Long Transfusion") versus <60-minute infusion ("Short Transfusion"). The IBS is an FDA-approved pathogen reduction technology that reduces the risk of transfusion-transmitted infections by inactivating a broad range of pathogens such as viruses, bacteria and parasites that may be present in donated blood. This technology is the standard of care processing for all platelet products collected by the Department of Transfusion Medicine (DTM), implemented January 14th, 2016. The 4-HOUR infusion duration was selected as the maximum infusion time since it is undesirable for components that contain red cells to remain at room temperature longer than 4 hours, and since it is generally recommended for components to complete transfusion within 4 hours by the FDA-recognized AABB *Circular of Information*

(https://www.fda.gov/downloads/BiologicsBloodVaccines/GuidanceComplianceRegulatoryInformation/G

uidances/Blood/UCM364587.pdf, accessed 11/07/2017). Sixty-minutes was selected for the maximum duration for the "Short Transfusion" based on retrospective data on platelet transfusion durations and to proscriptively not exceed the 300 mL/hour ("or as tolerated") rate recommended by the AABB Technical Manual (18th edition). As each transfusion will use a half-SDP, and since each full SDP is no greater than 390 mL, the maximum volume in each product issued within this protocol will not exceed 195 mL; thus, ensuring that the slowest infusion rate allowed within this protocol for the "Short Transfusion" does not exceed 195 mL/hour (that is, is not prescriptively forced to exceed the 300 mL/hour recommended standard rate).

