APPENDIX B: Protocol Worksheet

The SOLID Platelet Study, Protocol #19-CC-0005

LONG Transfusion followed by SHORT Transfusion

INSTRUCTIONS:

- All CBCs should be collected in a 2 mL EDTA tube; please WASTE the first 1 mL at each sample collection
- CBC collection times may occur (+/-) 15 minutes of the target draw time
- Documenting 'EXPECTED TIME' is optional; it is provided as a reference tool for planning the CBC collection and transfusion START / STOP Schedule
- Please call [name] (DTM, Protocol PI) with any questions, concerns, or if you run in to any problems, at [contact].

		EXPECTED TIME	ACTUAL TIME	PLATELETS	HEMOGLOBIN	
		(Optional)		(10 ⁹ /L)	(g/DL)	
1.	PRE (0-HOUR)					
	i. START Long Transfusion AFTER CBC collect	tion				
	ii. Continue transfusing over 4-HOURS					
	iii. Gently Swirl Bag for 20 revolutions every	30-min				-
	A. CBC COLLECTION					
	B. LONG TRANSFUSION START					
2.	2-HOUR (1b) + 2-HOURS					
	A. CBC COLLECTION					-
3.	4-HOUR (1b) + 4-HOURS - STOP Long Transfusion B	EFORE CBC Collection				TOE
	A. LONG TRANSFUSION STOP					BEO
	B. CBC COLLECTION					COMPLETED
4.	6-HOUR (1b) + 6-HOURS				≤P	
	i. START Short Transfusion AFTER CBC Collection					Ē
	ii. Also serves as the PRE (0-HOUR) CBC for	the Short Transfusion Tr	ansfuse for no more			Ē
	than 60-minutes					
	iii. Gently Swirl Bag for 20 revolutions every	30-minutes				
	A. CBC COLLECTION					BY DTM
	B. SHORT TRANSFUSION START					>
5.	7-HOUR (4b) + 1-HOUR - STOP Short Transfusion					
	A. SHORT TRANSFUSION STOP					
6.	8-HOUR (4b) + 2-HOURS					-
	A. CBC COLLECTION					-
7.	10-HOUR (4b) + 4-HOURS	1			-	-
	A. CBC COLLECTION					-
8.	12-HOUR (4b) + 6-HOURS					
	A. CBC COLLECTION					
		1				

Print Name of RN(s) Completing form	Signature	Date
1)		
2)		

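### Section 6.3.1 permits study CBCs from the line infusing the platelets, with only a 1 mL discard and no record of draw site; any carry-over would mainly raise the Long AUC, the direction the test rewards

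*Combined protocol and SAP*

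**What the plan says.** Section 6.3.1 sets the sampling route: "The sample should be obtained via the patient's peripheral access device". Venipuncture or a central draw is allowed only when the peripheral line cannot be used. Each 2 mL tube is filled "after wasting the first 1ml of blood drawn", and the stated purpose is to "prevent a false reading by drawing the sample from the same line through which the patient is receiving the transfusion".

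The first two post-start samples have fixed windows: "2-HOUR CBC: Obtained +/- 15-minutes of the 2-HOUR mark after the infusion start time" and "4-HOUR CBC: Obtained +/- 15-minutes of the 4-HOUR mark after the infusion start time". Section 6.2.2 runs Long over 4 hours and Short within 60 minutes, by pump or gravity, without naming the line. For the Long 4-hour draw, Appendix B has "4-HOURS - STOP Long Transfusion" ahead of the CBC, and Appendix C also lists the stop above the CBC. Neither worksheet has a comparable instruction at the Long 2-hour draw, and neither has a field for draw site.

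The endpoint (Section 8.1) is the trapezoid AUC of the count above baseline at 0, 2, 4 and 6 hours, adjusted for platelets given. The interim test is one-sided at 0.01 favouring slow infusion (Section 7.1), and the final test is one-sided at 0.04 (Section 8.2).

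**The concern.** The protocol recognises that a sample from the infusing line can give a false count. The chance of that error differs between the two periods because it follows infusion duration. Long's 2-hour sample (105 to 135 minutes after start) falls mid-infusion. Short's infusion is over by 60 minutes, so its first post-start sample comes at least about 105 − 60 = 45 minutes later. Randomising the order does not balance an error tied to duration. Nor does the dose adjustment remove it, since that uses the platelets in the bag and not those left in the line.

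The product is over 100 times as concentrated as the blood of a patient with a count of 10 x10^9/L, and real increments in refractory patients are small. Very little carry-over could therefore look like a benefit of Long. With no draw site recorded, nobody could later tell whether a positive result was partly a sampling artefact.

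**Working it through.** **The plan's own figure.** Section 7.1 states power above 80% for a sign test with n = 24 and a 0.80 chance that a pair favours Long. At one-sided 0.04 the test rejects at 17 or more of 24; exact alpha is 0.032 and power 0.911. The statement reproduces, and this point does not affect it. What is exposed is the type I error and the effect estimate.

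**Inputs from the documents.** Full component above 4.4 x10^11 platelets (Section 6.2.2), so about 2.2 x10^11 per half-dose. Full component volume: "since each full SDP is no greater than 390 mL" (Section 2). Patient count taken as 10 x10^9/L (the no-bleeding threshold in Section 4.1). Refractoriness at CCI below 5000 (Sections 3.2 and 4.1).

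**Assumptions, not in the documents.** The carry-over fraction, the share of patients sampled from the infusing line, the SD of the paired AUC difference, and body surface area.

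**Product concentration.** 4.4 x10^11 / 0.390 L = 1,128 x10^9/L, as a minimum.

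**Effect on one sample.** Added count = f x (1,128 − 10). For f = 0.1% (2 µL in the 2 mL tube) this is 1.12 x10^9/L; for f = 0.5% (10 µL) it is 5.6 x10^9/L.

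**Scale of a real increment.** Increment = CCI x dose / BSA. At the eligibility limit, 5000 x 2.2 / BSA gives 5.0 to 6.9 x10^9/L for BSA 2.2 to 1.6 m². A 0.5% carry-over in one sample is thus about the whole increment.

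**Effect on the AUC.** With 2-hour spacing, net AUC = 1·y0 + 2·y2 + 2·y4 + 1·y6 − 6·y0, so the weights are −5, 2, 2 and 1. An error at 2 hours counts twice: 2 x 1.12 = 2.2 x10^9.h/L for 0.1% carry-over. If the limiting increment were held flat from 2 to 6 hours, the whole AUC would be 5 x 5.0 = 25 to 5 x 6.9 = 34 x10^9.h/L.

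**Effect on the test.** I simulated the one-sided signed-rank test with no true effect, 100,000 trials per setting: 12 pairs at 0.01 (reject at W ≥ 69), then 24 pairs at 0.04 (reject at W ≥ 212), normal differences, no futility stop. Carry-over was 0.1% in the Long 2-hour sample only.

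| Assumed SD (x10^9.h/L) | No carry-over | All patients affected | Half affected |
|---|---|---|---|
| 8 | about 4% | 33% | 14% |
| 10 | about 4% | 24% | 11% |
| 15 | about 4% | 15% | 8% |
| 25 | about 4% | 10% | 7% |

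**The shared 6-hour sample.** It ends the first period (weight +1) and is the baseline of the second (weight −5). An error e there shifts Long minus Short by e + 5e = +6e in Group A and by −5e − e = −6e in Group B. Its net effect depends on how much residue remains in each sequence, which the documents do not give.

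**The case against.** The strongest reply is that the protocol saw the hazard and acted on it. A discard precedes every CBC, and it may fully clear a static line. No line dead volume is given, so zero residual carry-over is compatible with the text. No section says which line carries the platelets; if it is not the sampled line, the problem does not arise. All of this stands. It means that bias is permitted, not shown. It does not establish that a 1 mL discard is enough while product may still be flowing at 2 hours, and without a draw-site record the question could not be settled afterwards.

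A reader might infer more than the documents support, in three ways:

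- **That only Long can be affected.** No flush is specified, so residue could reach Short's 2-hour sample or the shared 6-hour CBC. What is particular to Long is a draw during infusion.
- **That the 4-hour sample is as exposed as the 2-hour one.** Giving both 0.1% carry-over in every patient would take the error to about 63% at SD 10. But Appendix B reads "4-HOUR (1b) + 4-HOURS - STOP Long Transfusion" and places that stop before the CBC. The 4-hour draw thus follows the end of infusion and a discard, so equal carry-over is not a fair base case.
- **That one error rate is an estimate.** The SD and the carry-over fraction are both undocumented; only a range can be given.

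It is also fair to object to routine venipuncture. A block needs seven CBCs and a patient may have three blocks, often with counts below 10 x10^9/L. Section 7.1 already expects dropout from inability to tolerate blood draws.

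**Conclusion.** The concern holds as a gap in the sampling rule. Section 6.3.1 allows, and by its wording expects, sampling from the infusing line; the only safeguard is a 1 mL discard, and the draw site is not recorded. Only Long has a mid-infusion CBC, so residual carry-over would mainly act in favour of Long in a test that rejects in that direction.

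If 0.1% of the Long 2-hour sample were product, the AUC would rise by about 2.2 x10^9.h/L. A nominal error of about 4% would then become about 10% to 33% with every patient affected, or about 7% to 14% with half affected, over assumed SDs of 25 down to 8. These figures show sensitivity to a small contamination; they do not forecast what will happen. The documents do not support the conclusion that the design does inflate Long.

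**What to change.** 1. In Section 6.3.1, for both periods alike, state that study CBCs are drawn from existing access that is not carrying the platelets (a second peripheral line or a central lumen) where available. Keep venipuncture as a fallback.
2. Where only the infusing line is available, have the study team specify one sampling procedure that clears the line, applied and documented identically in Long and Short.
3. Add a draw-site field for every CBC to the Appendix B and C worksheets.
4. Prespecify a sensitivity analysis of the primary endpoint that excludes blocks whose Long 2-hour CBC came from the infusing line and, separately, those whose Long 4-hour CBC did.

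The cost is protocol and worksheet wording, some use of a second access, and a smaller n in the sensitivity analysis. Affected blocks are flagged, not lost, so the primary analysis keeps its planned size.

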6.3.2. Documentation and Results Review

Testing for HLA-alloimmune-mediated PTR and HPA-alloimmune-mediated PTR will be performed upon enrollment, if not previously completed prior to enrollment. Weight and platelet count of the platelet component will be documented concurrently in the DTM Transfusion Services Laboratory. Treatment monitoring, including transfusion duration, CBC collection times, platelet counts, etc., will be occur concurrently via *The SOLID Platelet Study Nursing Worksheets* (Appendices B and C), the electronic medical record system, Clinical Research Information System (CRIS), and the already operational "DTM Platelet Transfusion Summary" and "Patient Platelet Count Summary" SQL reports.

Orders and results will be tracked through CRIS. Should CRIS not be available, the NIH form 2803-1 will be completed and accompany the specimen; it will be filed in the patient's medical record.

To evaluate the frequency and extent of hemorrhagic complications, bleeding will be assessed by the modified World Health Organization bleeding scale (Appendix A). This will be done by the Principal Investigator (PI), the Lead Associate Investigator (LAI), or Associate Investigator (AI) using chart reviews for bleeding events one day prior to the Transfusion Blocks, the day(s) of the Transfusion Blocks, and one day following the Transfusion Blocks. This approach is deemed reasonable in the absence of a standardized or consensus method to evaluate bleeding in platelet transfusion clinical trials ³¹.

Long-term follow-up observations will not be necessary after the study's completion.

7. BIOSTATISTICAL CONSIDERATIONS

This is a two arm, randomized block study.

7.1. Sample Size and Study Design

We will determine the sample size using the Two-Stage Design. At the first stage, 12 subjects will be accrued. An interim analysis will be performed to compare the platelet count AUC values, adjusted for the absolute number of platelets transfused (adjusted platelet AUC), between the within-block treatment pairs. If the difference is significant at the 0.01 one-sided level favoring

the slow infusion technique, then accrual will cease and the null hypothesis rejected. At the interim analysis we will also perform a futility analysis. If the conditional power for rejecting the null hypothesis at the end of the study is less than 0.3, then accrual will cease. Otherwise, an additional 12 subjects will be accrued, bringing the total number of subjects to n=24. To account for dropouts, up to 30 subjects will be enrolled. Anticipated dropouts are due to inability to tolerate blood draws.

This design (n=24) has power >80% using the sign test on the matched pairs from the first block for each patient under the alternative hypothesis that the probability that a matched pair of adjusted platelet AUC values favors the test regimen is 0.80, assuming no tied observations ³². The actual analysis will use the Wilcoxon matched pair signed rank test. A mixed model analysis for multiple blocks per patient will be performed as a secondary analysis.

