5. RESPONSE CRITERIA

Statistically significant difference in the adjusted platelet increment area under the curve (AUC) obtained between 0-HOURS and 6-HOURS after the start of the platelet transfusion (Long Transfusion or Short Transfusion); this is determined at the interim and final analysis. The interim analysis will include a test of the null hypothesis of no difference in efficacy, using a threshold of significance of 0.01, with a threshold of 0.04 used for the final analysis. See *Study Analysis*, Section 8.2 for further details.

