8.2. Study Analysis

All subjects who receive one 12-HOUR block of Short and Long infusion duration of platelets will be included in the primary analysis. Every effort will be made to evaluate the subjects before transfusion as well as at 2-HOURS, 4-HOURS and 6-HOURS after starting each platelet dose infusion. Adverse events will be tabulated by severity and attribution to treatment and disease (transfusion reactions will be classified using the CDC NHSN *Hemovigilance Module Surveillance Protocol*, which may be accessed at https://www.cdc.gov/nhsn/pdfs/biovigilance/bv-hv-protocol-current.pdf).

Final statistical analysis will be performed once all 24 subjects have completed the end of study assessments and all data have been archived for analysis. An interim analysis will be conducted after 12 subjects have completed at least one 12-HOUR block of transfusions. The planned

Protocol Number: 19-CC-0005 PI: [name]. analyses will include descriptive statistics on the proportions of platelet response and 2-HOUR to 6-HOUR platelet increment AUC values, adjusted for number of platelets given. Hypothesis testing will utilize Wilcoxon matched pair signed rank test for the primary analysis. Mixed model analysis will be employed for multiple blocks per patient and reported descriptively.

The interim analysis will include a test of the null hypothesis of no difference in efficacy using a threshold of significance of 0.01, with a one-sided threshold of 0.04 used for the final analysis. The interim analysis will also include a futility analysis based on the conditional power for rejecting the null hypothesis at the final analysis given the interim results. The futility analysis reduces the type I error of the design.

Secondary analysis based on mixed effect regression, and logistic regression analysis will also be employed if deemed appropriate.

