8.3. Stopping Rules

At the interim analysis we will perform a futility analysis. If the conditional power for rejecting the null hypothesis at the end of the study is less than 0.2, then accrual will cease.

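### Sections 7.1 and 8.3 give different conditional-power cut-offs (0.3 and 0.2) for the same futility stop at the 12-subject interim analysis

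*Combined protocol and SAP*

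**What the plan says.** The protocol plans one interim analysis, after 12 subjects have completed a block (sections 7.1 and 8.2). Four sections bear on the futility part of it.

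- Section 7.1: "If the conditional power for rejecting the null hypothesis at the end of the study is less than 0.3, then accrual will cease". It then gives the other branch: "Otherwise, an additional 12 subjects will be accrued, bringing the total number of subjects to n=24".
- Section 8.3, Stopping Rules, applies to the same interim analysis, the same measure and the same action. It stops if conditional power "at the end of the study is less than 0.2, then accrual will cease". It gives no continuation branch.
- Section 5 describes the interim and final tests and refers onward: "See *Study Analysis*, Section 8.2 for further details".
- Section 8.2 describes a "futility analysis based on the conditional power for rejecting the null hypothesis at the final analysis given the interim results" but gives no cut-off. It adds: "The futility analysis reduces the type I error of the design".

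On the test, section 7.1 says "This design (n=24) has power >80% using the sign test on the matched pairs from the first block", under the alternative that 80% of pairs favor Long, and then "The actual analysis will use the Wilcoxon matched pair signed rank test". Section 8.2 also names the Wilcoxon test for the primary analysis and sets the final level at one-sided 0.04. No section states what effect is assumed for the 12 subjects not yet observed when conditional power is computed.

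**The concern.** A futility rule is meant to fix the decision to stop or continue before the data are seen, and that takes one number. Here two current sections give two. The section to which section 5 refers the reader gives none, and no statement of precedence settles it. Section 7.1 is the fuller text because it spells out both branches; section 8.3 is the one titled Stopping Rules. Either could be the intended source.

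If the interim conditional power were 0.25, a reader of 7.1 would stop accrual and a reader of 8.3 alone would see no ground to stop. Which number was meant would then be argued after the result was known. At stake are whether a second group of 12 subjects is enrolled and how large the trial is expected to be when Long offers little or nothing.

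**Working it through.** **Inputs from the protocol.** Interim at 12 subjects and final at 24 (7.1); interim efficacy level 0.01 one-sided (7.1); final level 0.04 one-sided (8.2); alternative of 0.80 for a pair favoring Long (7.1); cut-offs 0.3 (7.1) and 0.2 (8.3).

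**Assumptions, because the protocol is silent.** The effect for the remaining 12 subjects is taken as the design effect or the observed trend, with the null value as a third case for the sign test. For the Wilcoxon test the differences are taken as normal, with a shift of 0.842 SD so that 80% favor Long.

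**1. The plan's own power figure.** The sign test at n=24 and one-sided 0.04 rejects at 17 or more of 24 (exact level 0.0320). P(Bin(24, 0.80) ≥ 17) = 0.911, so the stated power above 80% is reproduced.

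**2. The planned Wilcoxon test.** The exact critical values are W+ ≥ 69 at n=12 (p=0.0081) and W+ ≥ 212 at n=24 (p=0.0394). With Z1 the standardized interim statistic, half the information in hand and a final critical value of 1.751, the normal approximation is

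CP = 1 − Φ[(1.751 − √0.5·Z1 − 0.5·θ)/√0.5],

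where θ = 3.226 at the design effect (normal differences) and θ = Z1/√0.5 at the observed trend. Setting CP to 0.2 and 0.3 gives these stopping boundaries:

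- Design effect: Z1 = −0.647 and −0.330.
- Observed trend: Z1 = 0.817 and 0.976.

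| Effect assumed for remaining subjects (method) | Null futility stopping, 0.2 vs 0.3 | Disputed range, null | Disputed range, true 0.80 | Power, 0.2 vs 0.3 |
|---|---|---|---|---|
| Observed trend (200,000 simulated trials, approximate CP) | 78.7% vs 82.9% | 4.2% | 1.1% | 0.967 vs 0.957 |
| Design effect (20,000 simulated trials, simulated CP) | 25.0% vs 32.3% | 7.4% | 0.3% or less | 0.982 for both |
| Design effect (normal approximation) | 25.9% vs 37.1% | 11.2% | not computed | not computed |

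The simulated design-effect range is known to about 1-2 percentage points. With logistic and Laplace differences as well as normal, two runs gave 6.9% to 9.0%.

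Null expected sample size is 24 − 12 × P(stop at the interim), for either reason:

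- Design effect: 24 − 12 × (0.250 + 0.008) = 20.9 with 0.2, and 24 − 12 × (0.323 + 0.008) = 20.0 with 0.3.
- Observed trend: 24 − 12 × (0.787 + 0.008) = 14.5 with 0.2, and 24 − 12 × (0.829 + 0.008) = 14.0 with 0.3.

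Type I error at the observed trend is 0.037 (0.2) and 0.035 (0.3), against 0.043 with no futility stop. At the design effect it is 0.041 to 0.044 with or without either threshold.

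**3. The sign-test planning model, exact.** Interim efficacy needs 11 or more of 12. After x of 12 favorable pairs, CP(x) = P(Bin(12, q) ≥ 17 − x).

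- Design effect, q = 0.80: CP(5) = 0.8¹² = 0.069; CP(6) = 12 × 0.8¹¹ × 0.2 + 0.8¹² = 0.275; CP(7) = 0.558. So 0.2 stops at 5 or fewer and 0.3 stops at 6 or fewer. The disputed range is the single result 6/12, with probability 22.6% under the null, 12.8% at a true 0.65 and 1.6% at 0.80.
- Observed trend, q = x/12: CP(7) = 0.067 and CP(8) = 0.393. Both thresholds stop at 7 or fewer.
- Null, q = 0.50: CP(9) = 0.194 and CP(10) = 0.387. Both thresholds stop at 9 or fewer.

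| Sign-test rule | Type I error | Power at 0.80 | Null expected N |
|---|---|---|---|
| No futility stop | 0.0331 | 0.912 | 23.96 |
| Design effect, 0.2 | 0.0331 | 0.911 | 19.3 |
| Design effect, 0.3 | 0.0324 | 0.907 | 16.6 |
| Observed trend, either | 0.0286 | 0.878 | 14.3 |

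**4. Which choice matters more.** On the Z1 scale, going from 0.2 to 0.3 moves the boundary by 0.317 (design effect) or 0.159 (trend). Going from the design effect to the observed trend moves it by 0.817 + 0.647 = 1.464 at the 0.2 cut-off and by 0.976 + 0.330 = 1.306 at 0.3.

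**The case against.** The strongest reply is that the two sections can be obeyed together. Section 8.3 says only when to stop; it never requires accrual to continue at 0.2 or above. Section 7.1 supplies the continuation branch, so stopping below 0.3 satisfies both texts and continuing at 0.25 would breach 7.1. This stands, and it rules out the stronger reading that the futility rule cannot be executed. It does not show that 0.3 was the number intended, and a reader who goes to the section titled Stopping Rules would apply 0.2.

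A reader might also infer a threat to the trial's validity. The calculations do not support that. A futility stop can only remove rejections, as section 8.2 notes, and the power loss from either threshold is small when conditional power uses the design effect or the observed trend.

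A reader might take the sign-test figure of 22.6% as the size of the problem. That test supports the power statement only, and the figure needs the design effect as well; at the observed trend or under the null the disputed range is empty. The Wilcoxon figures are the relevant ones.

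Finally, it is tempting to say that the test behind conditional power is unspecified. Section 8.2 ties conditional power to rejection at the final analysis and names the Wilcoxon test for it, so the test follows from the text. Only the effect assumed for the remaining subjects is missing.

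**Conclusion.** The inconsistency is real and on the face of the current text: one look, one measure, one action, two cut-offs, and no statement of which prevails. Its practical size is modest. For the Wilcoxon test with normal differences, the thresholds disagree in about 4% of null trials (observed trend) to about 7-11% (design effect), which is roughly half a subject to one subject of null expected sample size on the simulated figures. At the 0.80 alternative they disagree in about 1% of trials or fewer, and power differs by at most about 1 point.

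Type I error is not inflated by either threshold, and the stated power above 80% holds with both, provided conditional power uses the design effect or the observed trend. That proviso matters: with conditional power computed under the null, sign-test power falls to 0.553 whichever threshold is used. That loss comes from the unstated assumption about the remaining subjects, which is a separate point, and not from the clash between 0.2 and 0.3.

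This is a should-fix correction affecting early stopping and expected sample size, not a threat to validity. The documents do not show which threshold is the right one.

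**What to change.** Before the interim look, the sponsor confirms the threshold it intended and states that one number in both 7.1 and 8.3; alternatively, one section states it and the other refers to it.

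In the same edit, add a sentence to 8.2 giving the effect assumed for the remaining 12 subjects, with conditional power computed for the final Wilcoxon test at one-sided 0.04. The futility rule should not be rewritten as a sign-test count, because that would base it on a different test from the final analysis.

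The cost is one corrected number and one added sentence, with no extra patients or data. The edit has its full value only if made before anyone has seen the interim result.
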